2.4 Rationale for Using the itouch Sure Pelvic Floor Exerciser

After consideration of the recommendations made by the Food and Drug Administration (FDA) at a meeting in October 2013, the itouch Sure Pelvic Floor Exerciser has been selected since it is a 510 (k) approved device in the USA. The comparator device is cleared by the FDA through the 510 (k) premarket notification process (K103698) and also CE Mark approved in Europe.

The iTouch Sure Pelvic Floor Exerciser was specifically selected since its intended use is very similar to the Neurotech Vital Compact device. The iTouch device is intended to provide electrical stimulation and neuromuscular re-education for the purpose of rehabilitation of weak pelvic floor muscles for the treatment of stress, urge and mixed urinary incontinence in women. In addition, the device is intended for home use by the patient with a pre-set programme for stress incontinence with a compliance monitor. In this study the itouch device will be used daily, as recommended by the manufacturer.

There are no significant additional risks related to the treatment of the patients with the itouch Sure Pelvic Floor Exerciser. Previous studies with vaginal electrodes have reported isolated incidents of vaginal irritation and infection. (Sand *et al* 1995)

2.5 Rationale of a Single-Blind Study Design

The study is considered single-blind as the subjects will be randomised to either the Neurotech Vital Compact device or the itouch Sure Pelvic Floor Exerciser. Since the two devices will be described in detail in the patient information sheet, the patients will know to which device they have been randomised, i.e. the Neurotech Vital Compact device delivers electrical stimulation through external electrodes and the itouch Sure Pelvic Floor Exerciser delivers electrical stimulation through an internal vaginal probe. This should not introduce any bias since patients would not have an expectation that the new device (Neurotech Vital Compact device) is better than the existing active control device (itouch Sure Pelvic Floor Exerciser).

The site personnel who allocate the devices, perform the device training at baseline and monitor the device compliance at the follow-up visits will not be blinded, but the personnel who perform the follow-up assessments will be blinded.

Verification to ensure that this blinding is maintained will be assessed at the monitoring visits.

2.6 Risk/Benefit of the Neurotech Vital Compact Device

2.6.1 Residual Risks Identified in Risk Analysis Report

As part of the risk analysis process conducted during development, all identified risks were subjected to review and were either eliminated or reduced to 'as low as reasonably possible' (ALARP) by changes in process, documentation and planned user training.

Potential risks under these ALARP categories include manufacturing, labelling, storage and user error problems.

2.6.2 Risks Associated with Participation in the Clinical Study

There are no anticipated additional risks to involvement in this clinical study than would be expected for normal treatment of this condition with alternative NMES devices with the possible but unlikely exception of patient sensitivity to the constituent materials of the garment/device materials. However, there is no reason to suspect that any reaction would occur or that there would be any subsequent long term health problems. All of these materials have been extensively used and documented for their biocompatibility with human skin. The garment and devices will be used in accordance with the Instructions for Use.

2.6.3 Possible Interactions with Concomitant Medical Treatments

There is no reason to suspect that NMES treatment would cause any interaction with concomitant medications. A full list of conditions contraindicated for use with NMES is documented in the Instructions for Use and subjects with these conditions are excluded via the inclusion/exclusion criteria for the study.

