	
epilepsy.
 
• Subjects with any bladder abnormality that would affect the urinary flow through the lower urinary tract including symptoms of a urinary tract infection, abnormal bladder capacity (e.g., >300 cc), post void residual volume >200 cc, spastic bladder, vesico-ureteral reflux or bladder stones.• Subjects with a blood clotting disorder or who are taking anti-coagulant medications.• Subjects who have previously had any urogynaecological related surgery that would affect the pelvic floor muscles or urinary flow through the urethra (excluding hysterectomy).• Subjects who have previously had pelvic floor radiation.• Subjects who have previously been treated for stress incontinence with injectable bulking agents and/or vaginal probes within the past 6 months.• Subjects with a clinical diagnosis of prolapse greater than Stage 2.• Subjects who are pregnant or could be pregnant.• Subjects who are less than 6 months post-partum or who are lactating.• Subjects who have any conductive intra-uterine devices or metal implants in the pelvic area, including hip and lumbar spine.• Subjects with pelvic pain or fibromyalgia or paravaginal defect.• Subjects with an active implanted medical device (e.g. pacemaker, insulin pump) or conditions that may be adversely affected by electrical stimulation (e.g. cardiac arrhythmias).• Subjects with a current or active history of pelvic cancer and/or subjects with a life expectancy of less than 12 months.• Subjects who are currently involved in any injury litigation claims.• Subjects who have participated in a clinical study in the last 3 months or any previous clinical study with Bio-Medical Research Ltd.• Subjects who have been committed to an institution by virtue of an order issued either by the courts or by an authority.
Study Sites:	Approximately 12 USA sites
Number of subjects planned:	Approximately 180 subjects (90 subjects per group).
Target population:	The patient population will be females with stress incontinence.

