6.3 Exclusion Criteria

1. Subjects who have an existing medical condition that would compromise their participation in the study, e.g. reduced sensory perception in the contact area of the stimulation electrodes; scars or vaginal tissue wounds, lesions or inflamed/infected areas in the contact area of the stimulation electrodes; vaginal bleeding between menstrual periods; uncontrolled diabetes.
2. Subjects who have a physical condition that would make them unable to perform the study procedures, e.g. pelvic or hip surgery within the past 6 weeks.
3. Subjects who have been diagnosed with Chronic Obstructive Pulmonary Disease (COPD).
4. Subjects with a history of an underlying neurological condition, e.g. Multiple Sclerosis, Parkinson's disease, epilepsy.
5. Subjects with any bladder abnormality that would affect the urinary flow through the lower urinary tract including signs or symptoms of an active urinary tract infection, abnormal bladder capacity (e.g., $>300 \text{ cc}$), post void residual volume $>200 \text{ cc}$, spastic bladder, vesico-ureteral reflux or bladder stones.
6. Subjects with a blood clotting disorder or who are taking anti-coagulant medications.

7. Subjects who have previously had any uro-gynaecological related surgery that would affect the pelvic floor muscles or urinary flow through the urethra (excluding hysterectomy).
8. Subjects who have previously had pelvic floor radiation.
9. Subjects who have previously been treated for stress incontinence with injectable bulking agents and/or vaginal probes within the past 6 months.
10. Subjects with a clinical diagnosis of prolapse greater than Stage 2.
11. Subjects who are pregnant or could be pregnant.
12. Subjects who are less than 6 months post-partum or who are lactating.
13. Subjects who have any conductive intra-uterine devices or metal implants in the pelvic area, including hip and lumbar spine.
14. Subjects with pelvic pain or fibromyalgia or paravaginal defect.
15. Subjects with an active implanted medical device (i.e. pacemaker, insulin pump etc.) or conditions that may be adversely affected by electrical stimulation (e.g. cardiac arrhythmias).
16. Subjects with a current or active history of pelvic cancer and/or subjects with a life expectancy of less than 12 months.
17. Subjects who are currently involved in any injury litigation claims.
18. Subjects who have participated in a clinical study in the last 3 months or any previous clinical study with Bio-Medical Research Ltd.

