- Do not use the device if you have any implanted metal devices in the abdominal or pelvic areas, for example hip prostheses.

Warnings:

- Stimulation should not be applied across or through the head, directly on the eyes, covering the mouth, on the front of the neck, (especially the carotid sinus), or from electrodes placed on the chest and the upper back or crossing over the heart.
- Application of electrodes near the thorax may increase the risk of cardiac fibrillation.
- Do not apply stimulation across the chest, because the introduction of electrical current into the chest may cause rhythm disturbances to the heart, which could be lethal.
- Do not apply stimulation over open wounds or rashes, or over swollen, red, infected, or inflamed areas or skin eruptions (e.g. phlebitis, thrombophlebitis, varicose veins).
- Do not apply stimulation over, or in proximity to, cancerous lesions.
- Do not apply stimulation in the presence of electronic monitoring equipment (e.g. cardiac monitors, ECG alarms), which may not operate properly when the electrical stimulation device is in use.
- Do not apply stimulation when in the bath or shower.
- Do not apply stimulation while driving, operating machinery, cycling or during any activity in which electrical stimulation can put the patient at risk of injury.
- Do not use in close proximity to shortwave or microwave therapy equipment which may produce instability in the stimulator output.
- Wireless communication equipment such as wireless home network devices, mobile phones, cordless telephones, base stations and walkie-talkies of between 1W to 10W can affect this equipment and should be kept a distance of least 2.3 to 7.3 metres away from the device.
- Use this device only with the garments, leads, electrodes, and accessories recommended by the manufacturer.
- Always ensure that the charger/power supply is positioned so that it is easy to unplug the power supply from the socket.
- To isolate this equipment from the mains, the charger/power supply plug should be removed from the socket.
- Apply stimulation only to normal, intact, clean, healthy skin.
- Do not attach any cables or connectors to Vital Compact, other than those supplied by **neurotech®**. Never connect any computer leads to the controller.

Precautions:

- The long-term effects of electrical stimulation are unknown.

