14.12 Appendix XII. itouch Sure Pelvic Floor Exerciser Instructions for Use

Instructions for Use

itouchsure

PELVIC FLOOR EXERCISER

IMPORTANT: Read this manual carefully before starting to use your itouch sure Pelvic Floor Exerciser. INAPPROPRIATE OR INCORRECT USE COULD BE UNSAFE.

This user manual is provided to you as part of your participation in a clinical study. Please only use the iTouch sure as directed by your study doctor

Caution: U.S. Federal Law restricts this device to sale by or on the order of a licensed healthcare practitioner.

Support

Please call your study doctor if you have any questions.

TABLE OF CONTENTS

CONTENTS OF PACKAGE	3
Before you use itouch sure for the first time	3
CONTRAINDICATIONS, WARNINGS AND PRECAUTIONS	4
ITOUSH SURE INDICATIONS FOR USE	5
TREATING URINARY INCONTINENCE	6
HOW TO SET UP AND USE itouch sure	7
ITOUSH SURE "SMART FEATURES"	9
ITOUSH SURECONTROLS	11
SCREEN DISPLAYS	14
Treatment	16
BATTERY USE	17
ITouch SURE CLEANING AND STORAGE	18
TROUBLESHOOTING	19
PRODUCT SPECIFICATIONS	19
PROGRAM SETTINGS	20

CONTENTS OF PACKAGE

Itouch Sure Control Unit
itouch sure Electrode
Connecting lead wire
Four AA batteries
Instruction booklet
Storage pouch

Before you use itouch sure for the first time

An examination of the vaginal tissue should be completed prior to initial treatment to rule out any contraindications, establish the baseline tissue condition and assess the physiology discussed below. Pelvic floor stimulation may not be successful if the urethra has excessive scarring or if there is significant denervation of the pelvic floor. The neuromuscular structures involved in urine storage must also be at least partially preserved. Patients with intact sacral reflex arcs and some innervation of the pelvic floor may benefit from pelvic floor stimulation.

The itouch sure unit must only be used in accordance with the advice of your treating physician. Be sure to read the instructions included in this booklet to supplement the information provided to you by your physician.

CONTRAINdications, WARNINGS AND PRECAUTIONS

Contraindications

Should not be used if you have any of the following conditions:

If you have a heart pacemaker or a rhythm problem

If you are pregnant or trying to become pregnant

If you have been diagnosed or treated for cervical, or any pelvic, cancer

If you have, or have had epilepsy

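### Two exclusion criteria are narrower than the device manuals: exclusion 13 omits abdominal metal, so the assurance in Protocol 2.6.3 is not fully true, and exclusion 16 omits past pelvic cancer

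*Protocol*

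**What the plan says.** Section 2.6.3 belongs to Section 2.6, the risk/benefit account of the Vital Compact. It points to the Instructions for Use for the list of contraindicated conditions and states that "subjects with these conditions are excluded via the inclusion/exclusion criteria for the study".

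On metal implants, the Vital Compact manual (Appendix XI, Contraindications) says: "Do not use the device if you have any implanted metal devices in the abdominal or pelvic areas", with hip prostheses as its example. Exclusion 13 in Section 6.3 covers conductive intra-uterine devices and "metal implants in the pelvic area, including hip and lumbar spine". The synopsis has the same wording.

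On cancer, the itouch manual (Appendix XII, Contraindications) tells a woman not to use the device "If you have been diagnosed or treated for cervical, or any pelvic, cancer". Exclusion 16 covers "Subjects with a current or active history of pelvic cancer", together with short life expectancy. Two neighbouring criteria bear on past cancer. Exclusion 8 reads "Subjects who have previously had pelvic floor radiation". Exclusion 7 removes women with earlier urogynaecological operations affecting the pelvic floor or urethral flow, but exempts hysterectomy.

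Section 2.8 argues that the itouch adds no risk in this study because it is used as its manual directs. It makes no statement about eligibility.

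**The concern.** Section 2.6.3 gives the reader, including an ethics board, a reason not to check the criteria against the manual. If a criterion is narrower than the manual, that reassurance is wrong on that item. A site that follows only the named criteria could then randomise a woman whom one device's manual tells not to use it.

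The manuals cannot be set aside as generic labelling, because each states that it was written specifically for this study. Section 2.6.4 also counts the Instructions for Use among the means of reducing risk. What is at stake is the safety of a woman with an unnamed contraindication who treats herself at home for up to 12 weeks, and the accuracy of a statement in the protocol. It is not the size or the analysis of the trial.

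**Working it through.** The plan gives no figure to reproduce. The check sets each entry under the Contraindications heading of each manual against the criteria in Sections 6.2 and 6.3.

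**Vital Compact manual (Appendix XI): 3 entries**

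| Contraindication | Criterion | Match |
|---|---|---|
| Pacemaker, defibrillator, other implanted electronics | Exclusion 15 | Yes |
| Pregnancy | Exclusion 11 | Yes |
| Implanted metal, abdomen or pelvis | Exclusion 13 (pelvis, hip, lumbar spine) | In part |

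Two of three are matched and one is narrower. The manual's own example, a hip prosthesis, is covered, and the lumbar spine goes beyond the strict pelvis. Metal elsewhere in the abdomen is not named. The first half of exclusion 15 concerns active implants, so it does not name passive abdominal metal either.

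**itouch manual (Appendix XII): 10 subject conditions** (the line on driving concerns an activity and is set aside)

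| Contraindication | Criterion | Match |
|---|---|---|
| Pacemaker or rhythm problem | Exclusion 15 | Yes |
| Pregnant or trying to be | Exclusion 11, inclusion 7 | Yes |
| Cervical or any pelvic cancer, diagnosed or treated | Exclusion 16 (current or active), 7 and 8 in part | In part |
| Epilepsy, now or past | Exclusion 4 | Yes |
| Active urinary infection | Exclusion 5 | Yes |
| Bleeding between periods | Exclusion 1 | Yes |
| Infection or lesions at the electrode site | Exclusion 1 | Yes |
| Diminished sensation | Exclusion 1 | Yes |
| Unable to understand or operate the device | Inclusion 10, training in 8.10.1 | Yes |
| Retention history or residual above 200 cc | Exclusion 5 | Yes; a resolved past episode is marginal and not claimed |

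One of ten is clearly narrower. To see what remains, follow one past case through the named criteria: cervical cancer treated some years ago by hysterectomy, without radiation, and now inactive.

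- Exclusion 16 does not apply, because the disease is neither current nor active.
- Exclusion 8 does not apply, because there was no radiation.
- Exclusion 7 does not apply, because hysterectomy is exempt.

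She passes every named criterion, yet the itouch manual tells her not to use the device.

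The two gaps differ in kind. The first falsifies part of 2.6.3. The second falls outside that assurance, which concerns the Vital Compact. It does not contradict 2.8 either; it only weakens that section's premise that the itouch is used as its manual directs.

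**The case against.** The strongest reply is that the criteria are not the only safeguard.

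- Exclusion 1 is an open clause on medical conditions that would interfere with participation. Exclusion 15 also reaches conditions that stimulation could make worse. An investigator could apply either one before randomisation to a contraindication in a stimulator manual.
- Every woman has a medical history and physical examination at Visit 1 (Section 8.9).
- The investigator and site team are trained on both devices at the initiation visit, before anyone is randomised (Sections 7.4 and 8.4).
- The protocol requires each device to be used as its manual directs (Sections 4, 7.1.1, 7.2 and 8.10.1), so treating a contraindicated woman would depart from those sections whatever exclusions 13 and 16 say.

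All of this stands and reduces the practical risk. It does not make 2.6.3 true as written. The open clauses rest on judgement at about 12 sites and name neither condition, so the history has no specific criterion to be checked against.

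A reader might go further and infer unequal loss between the arms. Each gap condition is contraindicated in one manual only: the itouch list is silent on metal implants, and the Vital Compact contraindications are silent on past cancer. A check made after allocation would therefore stop a woman in one arm and not in the other; she would not be replaced under Section 6.4, and if untreated she would leave the primary analysis set under SAP 2.1. The documents do not support this chain. No section describes a contraindication screen after allocation; Section 8.10.1 covers set-up and competence. The vaginal tissue examination in the itouch manual would not by itself reveal past cancer, and the Vital Compact manual gives only general advice to consult a clinician. On replacement the documents are mixed: Section 6.1 randomises until about 180 women have completed, while Sections 4 and 10.2 treat 180 as the number enrolled or recruited. The modified ITT rule is a separate matter that these criteria do not cause.

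**Conclusion.** The mismatch is real and its consequences are modest. Exclusion 13 is narrower than one of the three Vital Compact contraindications, so the assurance in 2.6.3 is not fully true. Exclusion 16 is narrower than one of the ten itouch subject conditions, which is a separate shortfall that contradicts no eligibility statement.

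The documents give no prevalence for either condition, so the number of women affected cannot be estimated. One such woman would be 1/90 = 1.1% of an arm, which shows only the weight of a single case. Nothing here changes alpha, planned power or the planned 180 subjects, and no differential loss is shown. The conclusion assumes that the 2.6.3 assurance refers to the Vital Compact manual, as its place in Section 2.6 indicates. The eligibility case report form and consent pages are not among the documents, so how often sites would catch these cases in practice cannot be judged. This is a minor safety and consistency correction.

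**What to change.** In Section 6.3 and the synopsis:

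- extend exclusion 13 to metal implants in the abdominal or pelvic area, keeping hip, lumbar spine and conductive intra-uterine devices;
- extend exclusion 16 to any diagnosis of, or treatment for, cervical or other pelvic cancer, keeping the life-expectancy clause.

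Alternatively, add one criterion that excludes any subject condition contraindicated in Appendix XI or XII. Either way, check it in every woman before randomisation, whichever device she later receives. Section 2.6.3 can then stand as written.

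The cost is a short protocol amendment, one line on the eligibility form and somewhat narrower eligibility. Sample size and analysis are untouched.

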2.6.4 Steps to be Taken to Control or Mitigate Risks

Full Failure Modes Effects Analysis (FMEA) has been conducted, in line with ISO14971, for all stages of design, manufacturing, storage, shipping and clinical use of this device. These have been continually updated at various stages during the introduction of this device aiming to identify and then address each potential risk in terms of severity of risk, potential frequency of occurrence (i.e. what could go wrong, what is the probability it could go wrong, what are the implications/severity if it does go wrong). Each identified risk was then subject to discussions over whether any action could be taken internally or through 'Instructions for Use' to reduce these risk scores to the ALARP (as low as reasonably possible) level felt to be acceptable.

2.7 Risk/Benefit Rationale

NMES is a safe treatment option for stress urinary incontinence. Once patients have been trained in the use of the device and application of the electrodes and associated garments, self-treatment is continued at home for up to 12 weeks without the need for prolonged interim hospital visits as part of routine care. The Neurotech Vital Compact device can be used with external electrode placement which is more acceptable for patients than the use of internal (vaginal or anal) electrodes or other internal devices.

Alternative non NMES treatment options such as Kegel pelvic floor exercises are not successful for many patients for a variety of reasons and may require regular motivational visits during the

training period. Pharmaceutical options for stress urinary incontinence are very limited and are not suitable for all patients.

Ultimately, surgical intervention provides relief for many patients but is obviously fraught with inherent surgical and anaesthetic risks not seen in less invasive therapies, in addition to hospital costs.

Therefore, there is a safety and cost benefit for the use of an external NMES device over alternative treatment options including surgery.

